15. DATA ANALYSIS

15.1. HIV Testing Uptake and Diagnoses

We will compare the age and sex of individuals who accept vs. refuse screening, using Student t and Chi-square tests. In addition, we will tally reasons for refusal to participate among those eligible, and compare eligible individuals who refuse vs. consent to study enrolment, using Chi-square or Fisher exact tests for categorical variables and Student t tests or Mann-Whitney U tests for continuous variables. Proportions of individuals who accept screening, are determined eligible, and enroll will be presented, with exact binomial CI.

We will compare the proportion of patients with the following outcomes in the observation and intervention periods: (1) tested for HIV infection; (2) newly diagnosed with prevalent HIV infection (i.e., HIV seropositive); (3) newly diagnosed with AHI. Because we expect 0 AHI cases in the observation period, we will use a combined outcome (i.e., newly diagnosed acute or prevalent HIV-1) to model the effect of the intervention, so that models will converge. We will conduct analyses on the individual-level data, using log-binomial generalized estimating equation (GEE) models to account for clustering by health facility. We will use a small-sample variance correction to handle the small number of clusters [63]. Models will include indicator variables for calendar time period to control for trends in HIV incidence in the study area.

We will compare baseline characteristics between individuals in the observation and intervention groups, using Chi-square or Fisher exact tests for categorical variables and Student t tests or Mann-Whitney U tests for continuous variables. Where imbalances are identified, we will control for these potential confounders in secondary analyses using GEE models as above. We will also conduct exploratory analyses to identify predictors of the combined outcome (i.e., newly diagnosed acute or prevalent HIV-1) in the intervention group, including age, sex, marital status, symptom or symptoms reported, sex of partners, number of partners, condom use, transactional sex work, and other risk behaviors. We will test for interactions between the intervention and other variables such as sex, and will present stratified analyses if meaningful interaction is observed. In analyses in which multiple null hypotheses are tested, p values will be adjusted using the Holm–Bonferroni method.

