health facilities and 5 pharmacies selected from the 26 health facilities and 26 pharmacies located in the study area, Mtwapa/Shanzu town (total population ~100,000) [33]. This area, known for its busy night life, sex work, and tourist industry, has been the site of a KEMRI HIV/STI Research Clinic since 2005 [39]. In this study, 3,602 adults were evaluated for prevalent HIV-1 infection (prevalence: 3.9%). Patients with fever were more likely to have prevalent HIV-1 infection than those without fever (9.1% vs. 3.3%, p<0.001), and HIV prevalence in febrile patients was higher than that of the general population in Kenya (5.6% in 2012) [21]. Since we excluded known HIV-positive patients, this prevalence among undiagnosed individuals is noteworthy. AHI was diagnosed in 5 of 506 patients with negative or discordant rapid test results who met risk criteria and were completely evaluated, for an AHI prevalence of 1.0%. Of the 5 AHI cases, 4 were diagnosed among the 241 patients with a documented fever (prevalence 1.7%), vs. 1 among 265 non-febrile patients (prevalence 0.4%, p=0.1). Malaria was confirmed by PCR in 4 (1.7%) of the 241 febrile patients [33]. Ongoing qualitative work based on interviews with these individuals over several weeks' follow-up reveals challenges with accepting the diagnosis, understanding the value of immediate treatment, and incorporating an HIV diagnosis into daily life ([name], in preparation); specific counseling may be required to optimize linkage and treatment outcomes for individuals with an AHI diagnosis.

In summary, this pilot study enabled us to test our novel approach to HIV testing for adults seeking health care, fine tune our intervention procedures, and set up a scalable intervention for use in Kenyan health facilities. We now propose to focus our HIV-1 RNA testing intervention on young adults 18-39 years of age, as the latest Kenya AIDS indicator survey shows a steady increase in HIV prevalence over this age range [40]. We will use our pooled-data consensus risk score algorithm (described above), as most likely to identify undiagnosed persons with AHI in a range of clinical settings.

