14. SAMPLE SIZE CONSIDERATIONS

The proposed work is powered for the stepped wedge design (Figure 2). Based on our pilot work, we estimate that 50%-60% of adults aged 18-39 at the six participating facilities will be eligible for the study and approximately 50%-80% of these will accept study participation. Our preliminary data shows that approximately 2% of young adults in this age range are diagnosed with prevalent HIV-1 infection under standard care, while approximately 5% will be newly diagnosed with acute (1%) or prevalent (4%) HIV-1 infection in the intervention period. If these estimates are correct, with 1,375 subjects in the observation period and 1,500 subjects in the intervention period and a type I error probability of 0.05, assuming a coefficient of variation (k) of 0.25, we will have >90% power to reject the null hypothesis that the HIV diagnosis rates for experimental and control subjects are equal [57]. This power is more than adequate for multivariable analysis related to the testing of this null hypothesis. Because facilities will not have the laboratory capacity to diagnose HIV before seroconversion during the observation period, the base rate of AHI detection is 0, and power to detect AHI during the intervention period is >90% even if AHI prevalence is well below 1%. The table below presents power for a range of coefficients of variation and acute/prevalent HIV prevalence in the intervention period, given our chosen sample size.

Table. Power for Evaluation of Null Hypothesis that HIV Diagnosis Rates are Equal

Diagnosed HIV, Observation Period	Diagnosed HIV, Intervention Period	Kappa	Power
2.0%	5.0%	0.20	94.4%
2.0%	4.3%	0.20	82.2%
2.0%	5.0%	0.25	93.0%
2.0%	4.3%	0.25	80.0%
2.0%	5.0%	0.30	91.4%
2.0%	4.3%	0.30	77.3%
2.0%	5.0%	0.35	89.4%
2.0%	4.3%	0.35	74.6%

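### Section 15.1 picks the secondary adjustment covariates from unclustered baseline tests instead of a fixed list, so chance can choose them and fever may be left out

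*Combined protocol and SAP*

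**What the plan says.** All of this is in section 15.1 of the combined protocol and SAP, except the fever result.

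- **Main analysis.** Individual-level data are analysed "using log-binomial generalized estimating equation (GEE) models to account for clustering by health facility", with a small-sample variance correction. On time: "Models will include indicator variables for calendar time period to control for trends in HIV incidence in the study area". No patient covariates are named.
- **Baseline comparison.** "We will compare baseline characteristics between individuals in the observation and intervention groups, using Chi-square or Fisher exact tests for categorical variables", with t or Mann-Whitney tests for continuous variables. No facility or calendar term enters these tests.
- **Selection rule.** "Where imbalances are identified, we will control for these potential confounders in secondary analyses using GEE models as above". No cutoff and no list is given.
- **Symptoms.** They appear only among the candidate predictors in an exploratory analysis within the intervention group.
- **Multiplicity.** The same paragraph ends: "In analyses in which multiple null hypotheses are tested, p values will be adjusted using the Holm–Bonferroni method". Whether the baseline tests are covered is not stated.
- **Fever.** Section 6.4.3, on the pilot: "Patients with fever were more likely to have prevalent HIV-1 infection than those without fever (9.1% vs. 3.3%, p<0.001". Reported fever is an item on the screening form (section 21.6), so it is recorded for every patient enrolled.

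**The concern.** The main model respects facility and calendar period, but the step that decides what enters the adjusted model respects neither. It also asks the wrong question of each covariate. Whether a characteristic happens to differ between periods says nothing about whether it predicts an HIV diagnosis. A predictor known in advance can be left out because its difference fell short of significance, and an irrelevant variable can enter by chance.

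This matters because case mix could differ between periods. Allocation is unblinded (section 8). Patients are enrolled once their facility's period is known. The two periods use different consents, and only intervention-period recruits see the explainer video (section 11.1.1). Unwillingness to be tested is a listed reason for not enrolling (section 21.6). The adjusted estimate is one of the places where a reader would look for reassurance, so its content should not depend on which tests came out significant.

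**Working it through.** **Inputs from the documents**
- Figure 2 (section 8): 23 facility-blocks of 125 patients, 11 observation (1,375) and 12 intervention (1,500). Site 1 has one observation and two intervention blocks; the other five sites have two of each.
- Section 14: 2% vs 5%, "a type I error probability of 0.05, assuming a coefficient of variation (k) of 0.25".
- Section 6.4.3: fever risk ratio R = 9.1/3.3 = 2.76. Fever share among fully evaluated risk-positive pilot patients: 241/506 = 47.6%.

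**Assumptions not in the documents:** covariate intraclass correlation ρ of 0.005-0.02; correlation c between blocks of one facility; 10 independent baseline tests at two-sided 5%; fever share p = 50%.

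**Step 1. Reproduce the plan's power.** I used the Hussey-Hughes variance on Figure 2 with eight categorical periods. The facility-intercept SD is 0.25 × 0.035 = 0.00875 and the patient variance is 0.035 × 0.965. This gives SE = 0.00872 and power Φ(0.03/0.00872 − 1.96) = Φ(1.48) = 93.0%, as stated. All eight rows of the table agree within 0.1 point. The plan's own clustering is therefore a facility effect that persists across blocks.

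**Step 2. How often one test flags a null covariate.** Divide every variance by p(1−p).
- Independent patients: 1/1375 + 1/1500 = 0.001394.
- Persistent facility effects: the net weight is 2/12 − 1/11 = 0.0758 at Site 1 and 2/12 − 2/11 = −0.0152 at each other site. The sum of squares is 0.00574 + 5 × 0.00023 = 0.00689, which is 4.94 times 0.001394.
- Block-specific effects: 1/12 + 1/11 = 0.1742, which is 125 times 0.001394.

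The variance inflation is D = 1 + ρ[c(4.94 − 1) + (1 − c)(125 − 1)], and the flag rate is 2[1 − Φ(1.96/√D)].

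| Structure | ρ = 0.005 | ρ = 0.01 | ρ = 0.02 |
|---|---|---|---|
| Facility-level (c = 1) | D 1.02, 5% | D 1.04, 5% | D 1.08, 6% |
| Drift (c = 0.8) | D 1.14, 7% | D 1.28, 8% | D 1.56, 12% |
| Independent blocks (c = 0) | D 1.62, 12% | D 2.24, 19% | D 3.48, 29% |

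Simulation over the Figure 2 layout agrees: 5.3-6.0%, 6.7-11.8% and 12-29% for the three rows.

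**Step 3. At least one chance selection.** With 10 independent tests at 5%: 1 − 0.95^10 = 40%. At the unrounded drift rates it would be 1 − (1 − 0.066)^10 = 50% to 1 − (1 − 0.117)^10 = 71%. If Holm-Bonferroni covers the 10 tests, it is about 5-7% with facility-level clustering.

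**Step 4. Fever.**
- Standard error of the crude difference: √(0.25 × 0.001394) = 0.01867. Flagging threshold: 1.96 × 0.01867 = 3.7 points.
- Chance that a true difference is flagged: Φ(0.03/0.01867 − 1.96) = 36% for 3 points and Φ(0.05/0.01867 − 1.96) = 76% for 5 points.
- At the first Holm step of 10 tests (0.05/10, z = 2.807), the threshold is 2.807 × 0.01867 = 5.2 points, and these chances fall to 11% and 45%.
- Shift in the risk ratio from an imbalance d: (R − 1)d / [1 + (R − 1)p]. At 3.7 points: 1.758 × 0.0366/1.879 = 3.4%. At 5.2 points: 1.758 × 0.0524/1.879 = 4.9%.
- On the planned risk ratio of 5%/2% = 2.5, that is 2.59 or 2.62.
- Without Holm, a fever share of 30% gives a threshold of 3.4 points and a shift of 3.9%; a share of 60% gives 3.6 points and 3.1%.

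**The case against.** The strongest reply is that the rule has limited reach. It governs a secondary model; the main model, its small-sample correction and the power figures are untouched. A covariate that barely differs between periods confounds little, which is why the shift from unflagged fever is only a few per cent. Adjusting for an imbalance that is present in the data is legitimate even if it arose by chance. The text writes no p-value cutoff, so selection by significance is inferred from the sentence before it. The plan also has other checks on selection. It approaches consecutive patients and records all screening outcomes (section 11.1.1), and it compares accepters with refusers (section 15.1). All of this stands, and it keeps the point small.

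The fever contrast also needs care. It comes from 3,602 pilot adults, whereas trial participants must score at least 2 on a scale that includes fever, and observation-period diagnosis depends on a clinician ordering a test. The risk ratio of 2.76 is therefore indicative only.

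A reader might infer more than the documents support:
- **That selection is largely chance**, with false flags of 12-29% per test. This requires blocks at one facility to be no more alike than blocks at different facilities. Section 8 has each facility serve as its own control, and the power table reproduces with persistent facility effects, which nearly cancel between periods.
- **That ignoring clustering explains the omission of fever.** It works the other way: it makes flagging more frequent. Fever can be omitted because the rule selects on imbalance.
- **That extra covariates would overload the log-binomial model.** No calculation supports this.

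**Conclusion.** The concern holds as a minor weakness of the secondary adjusted analysis. The rule ignores facility and calendar period, selects on imbalance instead of prognosis, and leaves both the threshold and the role of Holm-Bonferroni open, so two analysts following the text could fit different models.

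The excess of chance flags due to clustering is slight under the plan's own structure. It becomes appreciable only with drift between blocks, which the documents do not quantify. The roughly 40% chance of at least one spurious covariate comes mainly from the number of tests, which is assumed.

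Leaving out fever would probably move the secondary risk ratio by about 3-5%, depending on whether Holm-Bonferroni applies. That rests on a fever share near 50% and on the pilot risk ratio carrying over. It would not change the conclusion from an effect as large as the one planned.

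**What to change.** Replace the imbalance rule in section 15.1 with one prespecified secondary adjusted GEE: intervention, calendar period, age group, sex and reported fever, fitted whatever the baseline tests show. Report baseline characteristics descriptively by period and facility, without using tests to choose covariates.

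Age, sex and fever are already on the screening form, so no data collection, sample size or power figure changes. Fever is named because the protocol reports its association with prevalent HIV. The sponsor could argue for another item, such as genital ulcer, which carries the largest weight in the risk score. What matters is that the list is short and fixed before the data are seen.

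The downside is three extra coefficients in a secondary model with about 28 + 75 = 103 expected events.

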15.2. Linkage to Care

During the intervention period, participants with newly diagnosed HIV infection will be offered referral to our research clinic, and enrolled in ongoing HIV care cohorts. We will evaluate the following outcomes for prevalent HIV, acute HIV, and the combined outcome (acute or prevalent HIV infection): (1) proportion successfully linked to care by week 6; (2) proportion initiating ART by week 6 and month 3 following HIV diagnosis; (3) proportion with viral suppression (<1,000 copies/mL) by month 6 and month 12 following ART initiation. All proportions will be calculated with exact binomial CI, assuming independence between individuals. We will compare these outcomes between prevalent HIV and AHI cases using Pearson Chi square or Fisher exact tests, as appropriate. We will also compare these proportions to outcomes in HIV-infected partners using the same methods. As above, in analyses in which multiple null hypotheses are tested, p values will be adjusted using the Holm–Bonferroni method.

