Accounting for correlation within sites (i.e., facilities participating in the randomized trial), precision for the estimated rate of AHI detection is ±0.54%, assuming a prevalence of 1% and k=0.25; if AHI prevalence is 2%, precision will be ±0.81%. For the evaluation of impact and cost-effectiveness, precision is more important than power, since estimates will be used as ranges for modelling. Assuming 150 partners tested as a result of the aPS intervention, we can estimate their HIV prevalence with reasonable precision (binomial confidence limits [CL], 39.8%–56.3%, for 48.0% prevalence); in addition, we will have 80% power to detect a relative risk (RR) of 1.58 or higher for HIV infection in the partners of AHI patients (n=30), compared to partners of prevalent HIV patients (n=120). Assuming 75 new HIV diagnoses from the HIV-1 RNA testing intervention to detect acute and prevalent HIV infection, we can estimate the proportion attaining virologic suppression with reasonable precision (binomial CL, 69.2%–88.3% if 80.0% achieve suppression by month 12); we will have 80% power to detect an RR of 2.84 or higher for failure to suppress among AHI patients (n=15) compared to prevalent HIV patients (n=60).

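### Section 15.2 compares index cases with their own infected partners by tests for unrelated people; its exact intervals also need a sensitivity range for clustering

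*Combined protocol and SAP*

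**What the plan says.** Section 15.2 covers linkage to care by week 6, ART initiation by week 6 and month 3, and viral suppression by months 6 and 12. Three sentences matter:

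- For intervals: "All proportions will be calculated with exact binomial CI, assuming independence between individuals".
- For acute (AHI) against prevalent cases: "We will compare these outcomes between prevalent HIV and AHI cases using Pearson Chi square or Fisher exact tests, as appropriate".
- For index cases against partners: "We will also compare these proportions to outcomes in HIV-infected partners using the same methods". The methods meant are therefore unpaired chi-square or Fisher tests.

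Section 11.4.2 gives partners ID numbers that tie each of them to an index case in the dataset. Section 11.4.3 invites infected partners of intervention-period index cases into the same ART cohort and traces their partners in turn. The protocol summary places cohort follow-up at whichever of two research clinics is nearest.

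Elsewhere, Section 15.1 plans GEE "models to account for clustering by health facility", with a small-sample variance correction, and Section 15.3 plans Poisson GEE with the same correction. Both serve comparisons between the two study periods. In Section 14 the precision for AHI detection includes correlation within sites. The suppression precision in the same paragraph is plain binomial: "binomial CL, 69.2%–88.3% if 80.0% achieve suppression by month 12".

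**The concern.** Chi-square and Fisher tests take the two groups as independent samples. Here the second group is recruited through the first. An index case and a partner may share a household, a decision to disclose, the same clinic and the same counsellors, so their chances of linking, starting ART and suppressing are plausibly related. A test that ignores this uses the wrong variance for the difference, and the Holm–Bonferroni step does not repair that. A real index-partner difference could be missed, or the p-value could be too small where several partners hang on one index case.

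The intervals raise a separate and weaker concern. Patients from one facility share staff and referral arrangements, and cohort members share one of two clinics. If outcomes cluster at either level, an interval that assumes independence is too narrow. Section 14 says that, for the impact and cost-effectiveness work, precision matters more than power because the estimates supply ranges for modelling. A range that is too narrow would pass into the model.

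**Working it through.** **1. Reproduce the plan's figures (Section 14).**

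- Suppression: Clopper-Pearson limits for 60/75 are 69.17% and 88.35%; the plan prints 69.2–88.3%.
- Partner prevalence: 72/150 gives 39.78% and 56.30%; the plan prints 39.8–56.3%.
- AHI detection: 1.96 × √[p(1−p)/1500 + (kp)²/6] with k = 0.25 gives ±0.542% at p = 1% and ±0.814% at p = 2%; the plan prints ±0.54% and ±0.81%.

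All agree to within rounding. The AHI figure carries a between-site term and the suppression figure does not.

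**2. Index cases against partners, matched pairs.** Inputs: 75 index cases ("Assuming 75 new HIV diagnoses from the HIV-1 RNA testing intervention"); 150 partners tested at 48.0% prevalence, hence 150 × 0.48 = 72 infected. Assumptions: all 72 enter the comparison, each is matched to a different index case, and the true proportion is 80% in both groups. In units of p(1−p):

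- variance used by the unpaired test: 1/75 + 1/72 = 0.02722;
- true variance with within-pair correlation ρ: 0.02722 − 2ρ/75;
- ratio: 1 − 0.980ρ.

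| ρ | True / assumed variance | Simulated type I error (nominal 5%) |
|---|---|---|
| 0 | 1.00 | 5.0% |
| 0.1 | 0.90 | 3.9% |
| 0.3 | 0.71 | 1.9% |
| 0.5 | 0.51 | 0.7% |

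As a check, the normal approximation 2 × [1 − Φ(1.96/√0.902)] gives 3.9% at ρ = 0.1.

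**3. Several partners per index case.** Two infected partners of one index case, correlated at 0.1 to 0.5, inflate the variance of the partner proportion by 1.1 to 1.5. Suppose 36 index cases have two infected partners each (72 in all). The variance is then 1/75 + (1 + ρ_pp)/72 − 2ρ_ip/75, where ρ_pp is the partner-partner and ρ_ip the index-partner correlation.

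- ρ_pp = ρ_ip = 0.3: 0.02339, ratio 0.86, type I error about 3.4%.
- ρ_pp = 0.3, ρ_ip = 0.1: 0.02872, ratio 1.06, type I error about 5.6%.

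The direction therefore depends on the network structure and on which correlation is larger.

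**4. Single-proportion intervals.** The documents give no ICC for linkage, ART or suppression, so these are assumed values. Design effect = 1 + (m − 1) × ICC, with exact limits at n divided by the design effect, for p = 80% and n = 75. Six facilities give m = 12.5; two clinics give m = 37.5. The ICC of 0.016 applies the plan's k = 0.25 to the 20% failure rate: (0.25 × 0.20)²/(0.8 × 0.2) = 0.0156.

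| Clusters | ICC | Design effect | Limits | Simulated coverage of the plan's interval |
|---|---|---|---|---|
| none | 0 | 1.00 | 69.2–88.3% (plan) | 95.7% (six facilities) |
| 6 facilities | 0.01 | 1.115 | 68.5–88.8% | not run |
| 6 facilities | 0.016 | 1.18 | 68.1–89.0% | 93.8% |
| 6 facilities | 0.05 | 1.58 | 65.9–90.2% | 89.3% |
| 2 clinics | 0.016 | 1.57 | 65.9–90.2% | 89.4% |
| 2 clinics | 0.05 | 2.83 | 60.0–92.9% | 76.6% |

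Over six facilities the interval widens by 6% at ICC 0.01 and by 27% at 0.05.

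**The case against.** The strongest reply is that Section 15.2 is consistent with the rest of the plan. A reader might infer that it drops a clustering allowance which Sections 15.1 and 15.3 apply throughout. The documents do not support that. Those sections use GEE for their between-period models, but 15.1 also gives exact binomial intervals for screening and enrolment, and 15.3 also uses chi-square, Fisher and non-parametric tests for partner and network characteristics. Section 15.2 states its assumption openly.

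A reader might also infer that every interval in 15.2 is wrong. That is not shown either. The size depends on an ICC the documents do not give; the k of 0.25 concerns diagnosis and AHI detection. At ICC 0.01 to 0.016 over six facilities, each limit moves by about half a point to one point and coverage stays near nominal. For the 15 AHI cases alone (2.5 per facility), even ICC 0.05 gives a design effect of only 1 + 1.5 × 0.05 ≈ 1.08. GEE on 75 cases in six facilities would be fragile, especially if uptake nears 100%, whereas exact limits stay defined. The planned univariate and probabilistic sensitivity analyses of the model absorb some of the consequence.

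These points stand, and they argue against replacing the exact intervals. They do not rescue the index-partner test. Partners come only from index cases who accept partner services and permit contact, so tidy pairs are a simplification and the net direction is uncertain. Uncertain direction does not make an unpaired test valid when the links are known and recorded.

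**Conclusion.** The main point holds: the index-partner comparison ignores a dependence built in by recruitment, so its p-values are miscalibrated. With matched pairs and positive correlation the test is conservative, with type I error of 3.9% at 0.1 and 1.9% at 0.3 and a matching loss of power. It would be a mistake to read this as a risk of false positives in general; that needs several partners per index case and partner-partner correlation strong enough to outweigh the index-partner correlation. The pair layout and all correlations are assumptions.

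The secondary point holds conditionally: the exact intervals are likely too narrow if outcomes cluster. The effect is small at low ICC over six facilities, and material at ICC 0.05 or if the two clinics are the relevant clusters.

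The primary analysis is not touched. This is a minor, inexpensive improvement to secondary analyses.

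**What to change.** 1. In Section 15.2, replace the chi-square/Fisher comparison of index cases with infected partners by a binary GEE, or a comparison of proportions with cluster-robust variance. Take the index-partner network as the cluster: an index case, that person's partners, and their partners in turn. There are many such networks, so this avoids the six-cluster problem. State that sparse outcomes, such as no failures in one group, will be reported descriptively with exact limits.
2. Keep the exact binomial intervals as the main presentation. Beside them show limits at n divided by the design effect over a stated ICC range, for example 0.01 to 0.05, once for six facilities and once for two clinics. Label the ICCs as assumed.
3. Carry the wider limits into the linkage, ART and suppression ranges used in the Section 15.4 model.

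The cost is analysis code and a few sentences in 15.2. The links are already recorded, and no further participants, visits or data are needed. The price in the results is somewhat wider model ranges.
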